1.3.2.1. Efficacy assessments

PSA

Blood samples for PSA testing will be taken every 3 months (except at Visit 2 (Baseline, Day 1 Month 0) where PSA level is not required).

Biochemical Relapse

Biochemical Relapse definition: increased PSA >0.2 ng/mL confirmed by a second measurement performed 4 to 6 weeks later. The time-point at which the first elevated PSA measurement is >0.2 ng/mL is recorded will be deemed to be the time of BR.

To note, for the identification of BR; all PSA samples will be taken into account, even if several samples are within the same time windows.

Clinical disease progression

Clinical disease progression is defined as evidence of local/locoregional recurrence and/or lymph node involvement and/or distant metastases documented by relevant standard investigations (such as ultrasound (US) guided biopsy, X-ray, computed tomography (CT) scan, or magnetic resonance imaging (MRI) guided biopsy).

Survival status

Survival status will be recorded at each visit.

Serum Testosterone

Serum testosterone in the triptorelin treatment group will be recorded at baseline, 3, 6 and 9 months. It will be assessed both as a continuous and as a qualitative variable (< 50 ng/dL / ≥ 50 ng/dL).

Health-Related Quality of Life

Health-Related Quality of Life (HRQoL) will be assessed using the FACT-P questionnaire, version 4, and the 36-item short form (SF-36) health survey, version 2 in both treatment arms at Baseline, 9, 24, and 36 months..

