Should there be a suggestive country*treatment interaction or a centre(country)*treatment interaction, BRFS will also be analysed respectively by country/centre in order to describe any possible country/centre effect. Similarly, should there be a suggestive Gleason score*treatment interaction, BRFS will also be analysed by Gleason score categories (≤ 6 / $= 7$ / ≥ 8 , with ≤ 6 considered as the reference) in order to describe treatment effect within each subgroup.

Sensitivity analyses:

If a patient had at least two consecutive missing visits before the BR, a sensitivity analysis will be performed by censoring this patient at the date of the last visit preceding the missing consecutive visits (cf Section 3.2.10 for derived BRFS).

If patients died (whatever the cause) without BR, a sensitivity analysis will be performed by considering the death as an event (cf Section 3.2.10 for derived BRFS).

If lost to follow-up (prior to BR) is $\geq 5\%$. Baseline characteristics will be compared between groups of lost to follow-up and the other patients. If the lost to follow-up baseline characteristics differ from those of the other patients (as shown by 95 % CI), a sensitivity analysis will be performed excluding the lost-to follow-up patients.

Sensitivity analyses will be performed on ITT population on the first 61 BR events and repeated on the number of BR events observed until the end of the study if there is a difference of at least 5% of number of events (i.e. ≥ 65 events). The Log-rank test will be provided as well as the Cox Proportional hazard model. The interactions will be tested only if suggestive interactions were founded in the main analysis.

The primary efficacy analyses are summarised in the table below:

	ITT population		mITT population	PP population
	61 BR events	All BR events	All BR events	All BR events
Main analysis	X ⁽¹⁾	X	X	X
Sensitivity analysis 1 (censoring of patients with missing visits)	X	X ⁽²⁾		
Sensitivity analysis 2 (death as an event)	X	X ⁽²⁾		
Sensitivity analysis 3 (excluding lost-to-FUP patients)	X	X ⁽²⁾		

(1) Primary analysis

(2) Only if the number of BR events observed until the end of the study is different of at least 5% (i.e. ≥ 65 events)

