No BR and no clinical disease progression and new hormonal treatment (ie triptorelin or similar)	Censored	Date of last evaluable sample before the start of new hormonal treatment
No BR and no clinical disease progression and no premature withdrawal from the study	Censored	Date of last evaluable sample assessment
No BR and no clinical disease progression and patient premature withdrawal from the study or lost to follow-up	Censored	Date of last evaluable sample before withdrawal from the study or last contact
Clinical disease progression before BR	Censored	Date of clinical disease progression
No BR but death	Censored	Date of last evaluable sample assessment

- BRFS – Sensitivity Analysis 1

Event	Decision	Date of event or censor to consider for analysis
BR	Not censored	Date of BR (i.e. date of the first elevated PSA measurement is >0.2 ng/mL*)
At least two consecutive visits missing before BR	Censored	Date of last visit preceding the missing consecutive visits
No BR and no clinical disease progression and new hormonal treatment (ie triptorelin or similar)	Censored	Date of last evaluable sample before the start of new hormonal treatment
No BR and no clinical disease progression and no premature withdrawal from the study	Censored	Date of last evaluable sample assessment
No BR and no clinical disease progression and patient premature withdrawal from the study or lost to follow-up	Censored	Date of last evaluable sample before withdrawal from the study or last contact
Clinical disease progression before BR	Censored	Date of clinical disease progression
No BR but death	Censored	Date of last evaluable sample assessment

- BRFS – Sensitivity 2

Event	Decision	Date of event or censor to consider for analysis
BR	Not censored	Date of BR (i.e. date of the first elevated PSA measurement is >0.2 ng/mL*)
Death (whatever the reason) without BR	Not censored	Date of death
No BR and no clinical disease progression and new hormonal treatment (ie triptorelin or similar)	Censored	Date of last evaluable sample before the start of new hormonal treatment
No BR and no clinical disease progression and no premature withdrawal from the study	Censored	Date of last evaluable sample assessment
No BR and no clinical disease progression and patient premature withdrawal from the study or lost to follow-up	Censored	Date of last evaluable sample before withdrawal from the study or last contact
Clinical disease progression before BR	Censored	Date of clinical disease progression

- EFS

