5. CHANGES FROM PROTOCOL

The screened population have been defined as all patients with Visit 1 (Screening, Day - 14) performed and who have given informed consent.

The enrolled population have been defined as all patients from the screened population with visit 2 (Baseline, Day 1) performed.

The safety population have been defined as all randomised patients that have received at least one injection for patients from the triptorelin arm or that have undergone at least one day of active surveillance for patients from the active surveillance arm (patient that attended at least one visit after Visit 2 (Baseline, Day 1)) or with at least one collected safety data). The patients will be analysed according to the treatment received.

The mITT population has been added.

For primary endpoint, two other sensitivity analyses have been added:

- Censor the subjects if there are at least two missing consecutive visits before the BR.
- Consider death (whatever the cause) as an event.

The rules to apply if more than one record occurs within the same visit window have been changed for PSA and testosterone samples:

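### Sensitivity analysis 1 does not require the two-visit gap to fall directly before the biochemical relapse, so read literally it censors relapses that later PSA samples date well

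*SAP*

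**What the plan says.** Three places in the SAP describe the rule.

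- Section 3.2.1.1 (Sensitivity analyses) sets the trigger as "If a patient had at least two consecutive missing visits before the BR" and the action as "censoring this patient at the date of the last visit preceding the missing consecutive visits". The summary table that closes the section labels it "Sensitivity analysis 1 (censoring of patients with missing visits").
- Section 3.2.10 (table for BRFS, Sensitivity Analysis 1) has the row "At least two consecutive visits missing before BR", decision censored, with the date "Date of last visit preceding the missing consecutive visits". The row above it treats a biochemical relapse (BR) as not censored, at the date of the first elevated PSA. No order of precedence between the two rows is given.
- Section 5 records the addition as "Censor the subjects if there are at least two missing consecutive visits before the BR".

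Two definitions in Section 1.3.2.1 matter here. On timing: "Blood samples for PSA testing will be taken every 3 months". On the event: "increased PSA >0.2 ng/mL confirmed by a second measurement performed 4 to 6 weeks later", dated at the first of the two values.

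**The concern.** Missed visits make a relapse date doubtful when no evaluable PSA lies between the gap and the first elevated value. The trigger as worded does not make that distinction.

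Take a patient who misses Months 6 and 9, has PSA at or below 0.2 ng/mL at every visit from Month 12 to Month 30, and has a first elevated, later confirmed, PSA at Month 33. His relapse lies between Months 30 and 33. Under the literal wording he is censored at Month 3, which removes one confirmed event and 27 months (Month 30 minus Month 3) of documented relapse-free follow-up.

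The wording also treats patients unequally. The trigger needs a BR. A patient with the same Month 6 and 9 gap who completes the study without relapse or clinical progression falls under another row of the same table and is followed to his last evaluable sample. Under the literal rule, an early gap counts against a patient only if he later relapses.

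What is at stake is how this one robustness check can be interpreted. It could differ from the main analysis for reasons unrelated to the dating of relapses.

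**Working it through.** **The plan's own figure.** Section 1.3.4 assumes 36-month relapse probabilities of 40% and 20%, a two-sided 5% log-rank test and 90% power, and arrives at 61 BRs.

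- HR = ln(0.8)/ln(0.6) = 0.437.
- Schoenfeld: events = 4 × (1.960 + 1.282)² / (ln 0.437)² = 61.3. Power with 61 events is 89.9%.

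The figure of 61 reproduces, so it is used as the denominator below.

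**Inputs for the size of the problem.**

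- From the SAP: PSA every 3 months, giving 12 post-baseline visits to Month 36; relapse probabilities of 40% and 20%, as exponential hazards −ln(0.6)/36 = 0.0142 and −ln(0.8)/36 = 0.0062 per month; equal allocation.
- Assumed, because the SAP gives no figure: a missed-visit rate m of 5%, 10% or 20% per visit. Misses are either independent, or clustered with probability 0.5 of missing again after a miss.

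**Method.** 400,000 simulated patients per scenario. The relapse is detected at the first attended visit on or after it occurs. Among detected BRs, two shares are counted: those with a run of two or more missed visits at any time before detection (literal rule), and those where such a run ends at the detecting visit (gap immediately before).

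| Missed visits (assumed) | Literal rule, of 61 BRs | Gap immediately before, of 61 BRs | Difference |
|---|---|---|---|
| 5%, independent | 0.9 | 0.4 | 0.5 |
| 10%, independent | 3.2 | 1.4 | 1.8 |
| 20%, independent | 11.1 | 5.3 | 5.8 |
| 5%, clustered | 5.0 | 2.5 | 2.5 |
| 10%, clustered | 9.8 | 5.0 | 4.8 |
| 20%, clustered | 18.5 | 10.0 | 8.5 |

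**Hand check of the third column, independent misses.** On a long schedule, the share of relapses that fall in an interval spanning two or more missed visits is 1 − (1 − m)²(1 + 2m).

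- 5%: 1 − 0.9025 × 1.10 = 0.00725, or 0.4 of 61.
- 10%: 1 − 0.81 × 1.20 = 0.028, or 1.7 of 61.
- 20%: 1 − 0.64 × 1.40 = 0.104, or 6.3 of 61.

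The simulated values are slightly lower, as expected with only 12 visits: no two-visit gap can precede the earliest detections, and gaps that run past Month 36 yield no event.

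**Share that is well dated.** At 10% this is 1.8/3.2 = 56% with independent misses and 4.8/9.8 = 49% with clustered misses. These BRs have an attended visit between the gap and the relapse, and at most one missed visit directly before detection.

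**Power on the remaining events, at the design HR and 10% missed.** Independent: 88.3% (literal) against 89.2% (restricted). Clustered: 84.2% against 87.3%.

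**The case against.** The SAP never says that a gap anywhere before the relapse counts. A programmer could read the trigger as a gap leading up to the BR, and the reference to the missing visits in the singular sense of one gap fits that reading. The table also keeps its row for BR as not censored, without precedence. A reader might infer that the plan definitely discards the Month 33 relapse in the example. The text does not settle that. This objection stands, and it limits the point to a missing restriction. It does not remove the point: the literal wording permits the broad rule, and two programmers could produce different event counts.

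The SAP does not state the aim of this analysis. That it is meant to address uncertain relapse dates is an inference. A deliberately stricter analysis of patients with missed follow-up is conceivable, but it would not explain why patients with the same gap and no relapse are left in follow-up.

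The loss may be small. At 5% to 10% independent misses the difference is about 0.5 to 2 events. The analysis windows in Section 3.2.11 are contiguous. If missed visits are judged by those windows, missing Months 6 and 9 means no attendance from day 139 to day 321, which is 183 days. Gaps of that length may be rare, and the simulation did not model windows. This also stands.

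A reader might further infer that the primary result is weakened or that the hazard ratio would shift. Neither is supported. The relapses in question count in the main ITT analysis, and no hazard ratio under either rule was computed.

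**Conclusion.** The point holds as a defect of wording in one sensitivity analysis. All three statements of the rule omit the condition that the gap directly precede the BR. Followed literally, they censor relapses whose dates are not in doubt, while leaving comparable non-relapsing patients in follow-up.

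Under the assumed rates the literal rule censors about twice as many BRs as a rule limited to gaps immediately before the relapse. The extra loss is about 0.5 to 2 of 61 events at 5% to 10% independent misses, and about 2.5 to 5 if misses cluster. It becomes substantial only if visits are missed often. These sizes depend on missed-visit rates that the SAP does not give, on exponential relapse times at the design values, and on follow-up to Month 36.

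The primary analysis is untouched and no decision rule in the SAP depends on this analysis. It is a minor point, worth correcting because the correction is so cheap.

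**What to change.** In Section 3.2.1.1, in the Sensitivity Analysis 1 table of Section 3.2.10, and in Section 5:

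1. Censor only when two or more consecutive scheduled visits, with no evaluable PSA, are missing immediately before the first elevated PSA. This also settles which gap sets the date when a patient has several.
2. Censor at the last evaluable PSA sample before that gap. Most other censoring rows of the BRFS tables already use the last evaluable sample, and an attended visit without a PSA does not document freedom from relapse. If the gap begins at Month 3, the last sample is the screening one, and the existing rule in Section 3.2.10 moves a date before randomisation to the date of randomisation.
3. State in the table that this row takes precedence over the row that treats a BR as not censored.

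The cost is a few words in three places and the matching derivation code. No new data are needed and the primary analysis does not change.

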RAP Final Version 3 [22-JUL-2019]

15/248

CCI

1 Adverse events (AEs) will only be collected until Visit 5/Month 9; this corresponds to three months after the last triptorelin injection for those patients in the triptorelin group. After this visit, only AEs and SAEs related to triptorelin according to Investigator's judgement should be reported (with the exception of AEs resulting in death that should be reported until the end of the study).

Patients will not be withdrawn from the study if study medication is discontinued. Follow-up will continue for all patients every 3 months and for at least 36 months.

1.3.4. *Planned sample size*

It is planned to recruit 226 patients in approximately 10 centres in two countries (China and Russia) according to the Sample Size Determination.

The sample size estimation was based on the primary efficacy endpoint of BRFS. Assuming that with RP alone, the probability of biochemical (PSA) relapse as defined in Section 4.2.1 of the study protocol at 36 months after RP is 40% in high-risk patients (Section 2.1 of the study protocol, Table 1), and anticipating that immediate adjuvant hormonal therapy added to RP will reduce this probability to 20% (percentage considered to be clinically relevant), 113 patients per treatment group (226 in total) are required in order to detect such a difference using a two-sided log-rank test at a significance level of 5% and a power of 90%, assuming a common 1% exponential dropout rate (corresponding to an approximate 5% dropout rate per year).

These 226 patients are required to observe 61 BR in order to achieve 90% power. For patients with no sign of disease progression at 36 months post-randomisation, monitoring will continue until the 61 BR events are observed at the study global level. If the 61 events are observed before all patients complete the 36 months post-randomisation monitoring period, the study will be continued until those patients reach their 36 month visit (Visit 14).

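### Whether the BRFS result is tested for loss to follow-up depends on a low-powered baseline comparison of lost with other patients that is not split by arm

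*SAP*

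**What the plan says.** SAP section 3.2.1.1 lists three sensitivity analyses for BRFS. The third concerns loss to follow-up and has two conditions. First, at least 5% of patients must be lost before BR; the baseline characteristics of lost patients are then compared with those of all other patients. Second, "If the lost to follow-up baseline characteristics differ from those of the other patients (as shown by 95 % CI), a sensitivity analysis will be performed", and that analysis drops the lost patients.

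The SAP does not name the characteristics or say how many must differ. It does not say whether the interval is for the difference or for each group separately, and it mentions no split by arm. The summary table at the end of the section marks this analysis as planned at 61 events without repeating the baseline condition.

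The censoring table for BRFS in section 3.2.10 censors lost patients at the last evaluable sample before withdrawal or last contact. The other two sensitivity analyses deal with runs of missed visits before a BR and with death counted as an event.

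Section 1.3.4 gives the design: "113 patients per treatment group (226 in total) are required", with a dropout assumption described as "corresponding to an approximate 5% dropout rate per year".

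**The concern.** The main analysis assumes that a patient who is lost has the same later BR risk as patients still followed in his arm. Of the three sensitivity analyses, only the third addresses patients who are lost without a BR. If its second condition is not met, that assumption is never examined.

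The condition is a significance test in all but name. It has no margin for what counts as a relevant difference, and one of the two groups is small by construction. Failure to show a difference then mostly reflects how few patients were lost. In the other direction, an open list of characteristics, each judged at 95%, makes a chance finding likely.

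The comparison also asks the wrong question. Bias in the treatment comparison depends on who is lost in each arm. Opposite patterns in the two arms can cancel when all lost patients are set against all others. The trial is open, and only one arm receives injections, so reasons for leaving that differ by arm are plausible.

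**Working it through.** **1. The plan's own figures (section 1.3.4).** The inputs are a "two-sided log-rank test at a significance level of 5% and a power of 90"%, a BR probability "at 36 months after RP is 40% in high-risk patients", and treatment that "will reduce this probability to 20"%. With exponential times:

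- HR = ln(0.8)/ln(0.6) = 0.437.
- Events (Schoenfeld) = 4 × (1.960 + 1.282)² / (ln 0.437)² = 61.3. Power at 61 events is 89.9%.
- With 5% per year dropout and 36 months for everyone, P(BR observed) = 0.280, so 62 events need 62/0.280, about 222 patients. The planned 226 is within 3%.

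The design therefore reproduces, and its inputs can be used below.

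**2. How many patients are lost.**

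- Lowest number meeting the first condition: 0.05 × 226 = 11.3, so 12. The SAP states no denominator; I assume ITT.
- Expected number by Month 36 if all dropout counts as loss: dropout hazard η = −ln(0.95)/12 = 0.00427 per month; BR hazards λ = −ln(0.6)/36 = 0.01419 and −ln(0.8)/36 = 0.00620. Lost before BR per arm = 113 × η/(λ+η) × [1 − exp(−36(λ+η))]. This gives 12.7 (surveillance) + 14.5 (triptorelin) = 27.2.

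**3. Chance of missing a true difference in one characteristic.** Assume a 0.5-SD difference, n lost and 226 − n others, and a 95% CI of the difference. The standardised signal is δ = 0.5/√(1/n + 1/(226 − n)), and the chance of missing is approximately Φ(1.96 − δ).

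| Lost | δ | Missed (noncentral t) |
|---|---|---|
| 12 | 1.69 | 61% |
| 20 | 2.13 | 43% |
| 27 | 2.44 | 32% |

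If the condition instead requires two separate 95% CIs not to overlap, simulation gives 78%, 65% and 55%. For a binary factor at 60% versus 40% (CI of the difference, by simulation), it gives 69%, 57% and 49%. With 12 lost, 80% power needs a difference of about (1.960 + 0.842) × √(1/12 + 1/214) = 0.83 SD.

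**4. Chance of meeting the condition when nothing differs.** For k independent characteristics this is 1 − 0.95^k: 40% for k = 10 and 51% for k = 14.

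**5. The condition as a whole, with one true 0.5-SD difference among k.** P(not met) = P(miss that one) × 0.95^(k−1).

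| Lost | k = 10 | k = 14 |
|---|---|---|
| 12 | 0.611 × 0.630 = 38% | 0.611 × 0.513 = 31% |
| 27 | 0.320 × 0.630 = 20% | 0.320 × 0.513 = 16% |

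Much of the improvement over step 3 comes from chance findings in characteristics that do not differ.

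**6. Whether a one-sided worst case could replace the current analysis.** Count every lost triptorelin patient as a BR at the next 3-monthly visit and keep lost surveillance patients censored. Under the plan's assumptions, with dropout unrelated to prognosis, simulation shows power falling from about 87% to 27%. So 1 − 27/87, about 69%, of significant results are overturned although nothing is wrong.

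**The case against.** The strongest reply has four parts.

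- **A reader might infer that the SAP treats a non-significant comparison as proof that loss is harmless.** It does not say so. It only states when a supplementary analysis is run, and the ITT log-rank test stays primary. This part stands: the fault is an untested assumption, not a false claim.
- **The single-characteristic miss rates overstate how often the rule fails.** The SAP speaks of characteristics in the plural, and any one of them may meet the condition. This also stands, and step 5 is the fairer measure. It does not rescue the rule, because the lower failure rate comes partly from chance.
- **The expected loss of 27 is an upper figure.** Section 1.3.2.4 lists lost to follow-up as one of several withdrawal reasons, so loss in that narrow sense could be fewer. This stands too, but fewer lost patients make the comparison weaker.
- **The analysis being skipped is itself weak**, since it only drops censored patients. This is true, and is a reason to improve the analysis as well as free it from the condition.

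A reader might also infer that the rule lets through a materially inflated type I error. The documents do not support that. In an illustration with no treatment effect, opposite risk groups lost in the two arms and an assumed hazard ratio of 3 between them, the log-rank test rejected 5.9% of the time at 6% loss per arm, against 5.3% with no loss. With 4,000 replicates the standard error of that difference is about 0.5 points, so no inflation is clear. At 14% loss rejection was 8.0%, but the scenario is constructed and nothing in the SAP points to it. It shows only that opposite patterns need not trigger the comparison, which fired in 4.6% of those trials.

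**Conclusion.** The point holds as a defect in how a sensitivity analysis is triggered; the primary test is unaffected. With one true 0.5-SD difference among 10 to 14 characteristics, the analysis is skipped about 31% to 38% of the time at 12 lost and 16% to 20% at 27. With no difference at all, it is run by chance 40% to 51% of the time. The decision therefore carries little information about whether loss matters.

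These figures rest on assumptions that the SAP does not supply: the 0.5-SD difference, 10 to 14 independent characteristics, a CI of the difference, and 226 as denominator. The figure of 27 also needs all dropout to count as loss. That the comparison pools the arms is the natural reading of section 3.2.1.1, not an explicit statement.

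**What to change.** In section 3.2.1.1:

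- Delete the baseline-difference condition. Run the loss-to-follow-up sensitivity analysis of BRFS whenever loss before BR is at least 5%, and state the denominator.
- Tabulate the number, timing and baseline characteristics of lost patients by arm, as description only.
- Pre-specify a tipping-point analysis. Raise the assumed BR hazard after loss for lost triptorelin patients in steps, keep lost surveillance patients at their arm's hazard, and report the value at which the log-rank conclusion changes.
- Show the case in which all lost triptorelin patients relapse at the next visit only as the extreme end of that range, for the reason in step 6 of the working.

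The cost is SAP wording and one more set of tables from data already collected. A loss analysis will also be reported in some situations where the present rule would have skipped it.
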